11.14 Prior and Concomitant Medications

If a medication ended prior to first use of BVR-100/BES-100, then it is considered as prior medication.

If the medication ended on or after the first use of BVR-100/BES-100 or is ongoing, it is considered as concomitant medication.

11.15 Adverse Events

Any Adverse Event (AE) is defined as any effect that occurs or worsens after the first VR session until EOS will be summarized. Any events that occur after the time of signing the Informed Consent Form (ICF) and prior to the first VR session are termed as pre-treatment events.

Related Adverse Events include Possibly, Probably and Definitely Related Adverse Events.

UADEs are serious adverse effects caused by, or associated with a device which were not previously anticipated to occur. UADEs collected in CRF data will be summarized.

11.16 Columbia-Suicide Severity Rating Scale (C-SSRS)

The following outcomes are C-SSRS categories. The categories have been re-ordered from the actual scale to facilitate the definition of composite endpoints:

Category 1	Wish to be Dead
Category 2	Non-Specific Active Suicidal Thoughts
Category 3	Active Suicidal Ideation with Any Methods (Not Plan) without Intent to Act
Category 4	Active Suicidal Ideation with Some Intent to Act, without Specific Plan
Category 5	Active Suicidal Ideation with Specific Plan and Intent
Category 6	Actual Attempt
Category 7	Has subject engaged in Non-Suicidal Self-Injurious Behavior?
Category 8	Interrupted Attempt
Category 9	Aborted Attempt
Category 10	Preparatory Acts or Behavior

Suicidal Ideation – A “yes” answer at a visit to any one of the 5 suicidal ideation questions (categories 1-5) on the C-SSRS.

Suicidal Behavior – A “yes” answer at a visit to any one of the 5 suicidal behavior questions (categories 6-10) on the C-SSRS.

Suicidal Ideation or Suicidal Behavior – A “yes” answer at a visit to any one of the questions on the C-SSRS.

It is possible for subjects to have neither suicidal ideation nor suicidal behavior, or even to have both suicidal ideation and suicidal behavior.

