### 15.2. Analysis Populations

The effectiveness analyses will be based on the modified Intent-to-Treat (mITT) population, which includes all subjects who are randomized, have completed at least one VR session, and have a Baseline and at least one post-Baseline effectiveness measurement in CEQ. Additional analysis of the Per-Protocol (PP) population (defined as all subjects who have completed the 8-week intervention period without any important protocol deviations) is supportive, while the mITT population will be the primary analysis population. The primary effectiveness endpoint must achieve significance in the mITT to preserve type I error for the secondary endpoint.

The safety assessments will use the Safety population, which includes all subjects who are randomized and have completed at least one VR session.

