7.3 Safety Endpoints

- Incidence of AEs.
- Incidence of SAEs.
- Incidence of UADEs.
- Frequency of subjects with suicidal ideation or suicidal behavior based on the C-SSRS.

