10.3 Safety Population

The safety population consists of all randomized subjects who have completed at least one VR session.

The safety population will be used for the analysis of safety. Subjects will be analyzed as treated, regardless of the randomized treatment assigned, if this differs from that to which the subject was randomized.

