12.10.5 Columbia- Suicide Severity Rating Scale (C-SSRS)

Number and percentage of subjects without suicidal ideation or suicidal behavior, with suicidal ideation, with suicidal behavior, and with suicidal behavior or ideation will be presented by treatment groups based on ITT Population. All C-SSRS data will be listed based on all Enrolled population.

Above analysis details are specified in DDP Table 14.3.3.1 and Listing 16.2.8.1.

13 Changes to Planned Analyses

- 1 Protocol (section 12.3) specifies 'Baseline demographic and clinical characteristics will be compared between groups with the use of the two-sample t-test and the Mann–Whitney test for continuous measurements with and without normal distribution, respectively'. But the statistical testing for baseline characteristics is being waived as per the recent discussion with the sponsor.
- 2 Protocol (section 12.9) mentions an analysis about differences in the mean change from CGI-S baseline score in the CGI-I and PGI-I at Weeks 2, 4, 6, and 8. This analysis is waived as per the recent discussion with sponsor.
- 3 An additional exploratory endpoint number [7](#) regarding the number of required BVR-100 and BES-100 sessions completed, is added in the section 7.4 as per the decision by sponsor clinical team.
- 4 Sentence "to ensure a reliable estimate of the standard deviations to power a future trial with 90% and an expected effect size between 0.3 and 0.7" in section 4.2 Sample Size Justification is removed because it is for future study not for this current study.
- 5 Per-protocol population definition in section 10.5 is updated to consider only ITT population as per the recent discussion with sponsor.
- 6 Baseline clinical characteristics is updated to follow the baseline definition in section 11.10 as per the recent discussion with sponsor.
- 7 In section 10.4, mITT (Modified Intent-to-Treat) population is removed from analysis and ITT population (efficacy population) has been added as per sponsor request. This population will be used for primary and secondary endpoint analysis.

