Credibility / Expectancy Questionnaire (CEQ) scores	ITT Population	Primary: Descriptive summary, Independent t-test
	Per-Protocol Population	Supportive: Descriptive summary, Independent t-test
Secondary Endpoints		
Subject Retention Rate	ITT Population	Descriptive summary
Time-on-task		Descriptive summary
Exploratory Endpoints		
LSAS Overall & Subscores	ITT Population	Descriptive summary, Independent t-test
Responder Rate		Descriptive summary, Fisher's exact test
CGI-S Score		Descriptive summary
CGI-I Score		Descriptive summary
PGI-I Score		Descriptive summary
PHQ-9 Score		Descriptive summary
Safety Endpoints		
Adverse Events	Safety Population	Descriptive summaries on overall AE, relationship, severity etc.
C-SSRS		Descriptive summary

17 Change Log

Version	Author	Change Date	Description	Reviewer	Review Date
1.00	[REDACTED]	31-Jan-2024	First Approved Version	[REDACTED]	31-Jan-2024

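### SAP 11.16 counts non-suicidal self-injury (C-SSRS category 7) as suicidal behavior and includes it in the combined safety outcome

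*SAP*

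**What the plan says.** SAP 11.16 lists ten C-SSRS categories, noting that they were put in a different order from the scale so that composites could be defined. Categories 1-5 are ideation. Category 6 is an actual attempt, category 7 reads "Has subject engaged in Non-Suicidal Self-Injurious Behavior", and categories 8, 9 and 10 are interrupted attempt, aborted attempt and preparatory acts.

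Two rules follow. Suicidal behavior is a yes to "any one of the 5 suicidal behavior questions (categories 6-10) on the C-SSRS". The combined outcome is a yes to "any one of the questions on the C-SSRS".

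These rules feed the safety endpoint in SAP 7.3, "Frequency of subjects with suicidal ideation or suicidal behavior based on the C-SSRS", which Protocol 6.4 also names. SAP 12.10.5 tabulates four lines by arm: neither, ideation, behavior, and either.

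**The concern.** Section 11.16 contradicts itself. It labels an item non-suicidal and then counts it as a suicidal behavior question. Giving both the number of items and the range makes the inclusion explicit, so a programmer who follows the text will code it that way. Neither the SAP 7.3 endpoint nor the protocol extends suicidal behavior to non-suicidal self-injury, and SAP 13 lists no such change. Protocol 11.4.2 values the scale partly because it limits over-identification of suicidal behavior; this rule works the other way.

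Suicidal ideation or behavior is one of four named safety endpoints. In arms this small, one misclassified subject can decide whether an arm shows zero or some suicidal behavior, if that arm has no other case. The pilot is also meant to inform a later registration trial (Protocol 4.3).

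Three smaller mismatches in the safety text can be corrected in the same revision; no figure is claimed for them.

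- **(a) Analysis set.** SAP 12.10.5 puts C-SSRS on the ITT set. SAP 10.3 says "The safety population will be used for the analysis of safety", Protocol 15.2 says "The safety assessments will use the Safety population", and the SAP Section 16 summary table lists C-SSRS as a safety endpoint directly beneath the adverse-event row, which names the Safety Population.
- **(b) Period.** Protocol 15.4.3.2 asks for summaries over the whole time after Baseline and for each visit. SAP 12.10.5 states no period, and SAP 13 lists no change.
- **(c) AE onset.** SAP 11.15 covers events after the first VR session and events before it. An event that starts during that session falls in neither class. Protocol 15.4.3 covers that case, but SAP Section 2 gives the SAP precedence over the protocol's statistical section.

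**Working it through.** **Inputs.** Category labels and rules: SAP 11.16. Table lines: SAP 12.10.5. Planned arm of 20: SAP 4.2. Treated subjects at the January 2024 cutoff, 52: SAP 13. The documents do not give the split of the 52 by arm, so the splits below are assumptions.

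**1. The SAP's count of five.** Categories 6, 7, 8, 9 and 10 make 5 items. Without category 7 there are 4. The stated 5 is reached only by counting the item labelled non-suicidal.

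**2. Classification under each rule.** The corrected rule takes behavior as 6, 8, 9, 10 and either as 1-6 or 8-10.

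| Subject's yes answers | Rule | Neither | Ideation | Behavior | Either |
|---|---|---|---|---|---|
| Category 7 only | SAP | No | No | Yes | Yes |
| Category 7 only | Corrected | Yes | No | No | No |
| Category 7 plus any of 1-5 | SAP | No | Yes | Yes | Yes |
| Category 7 plus any of 1-5 | Corrected | No | Yes | No | Yes |

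The first kind of subject is wrong on 3 of 4 lines, the second on 1 of 4 (behavior).

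**3. Direction.** Ten yes/no items give 2^10 = 1024 answer patterns. The rules differ when category 7 is yes and 6, 8, 9 and 10 are all no, whatever the answers to 1-5: 2^5 = 32 patterns. In all 32 the SAP rule adds the subject to the behavior line. In the one pattern with no ideation it also adds the subject to the either line and removes the subject from the neither line. This count shows only the direction of the error; it says nothing about how often such answers occur.

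**4. Size per misclassified subject** on the behavior line, 100/n percentage points:

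- Arm of 20 (planned): 100/20 = 5.0
- Arm of 26 (52 split evenly, assumed): 100/26 = 3.8
- Assumed splits from 22:30 to 30:22: 100/30 = 3.3 to 100/22 = 4.5

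**The case against.** The case for leaving it is that little depends on the table. SAP 8.1 makes the safety analysis descriptive, with no test attached. All C-SSRS data are listed, so a subject with only category 7 could be found. Discontinuation under Protocol 11.4.2 depends on ideation items 4 and 5. Exclusion criterion 9 removes people with a lifetime suicide attempt, recent suicidal or self-harm ideation, a positive PHQ-9 item 9, or suicidal behavior on the C-SSRS at Screening or Baseline. The documents show no affected subject.

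All of that is true, and it limits the severity. It does not make the definition right. A listing does not correct a summary table. Criterion 9 does not name non-suicidal self-injurious behavior as such, and no entry criterion can exclude events that arise during the study.

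On the smaller points:

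- **(a)** Both sets require randomization and at least one VR session, both use actual treatment, and both number 52 at the cutoff. This is alignment only. The C-SSRS row of the Section 16 table has no population entry of its own in the text available, so its population is read from the layout.
- **(b)** The Data Display Plan, which was not available, may specify the period, and SAP 11.16 already defines each outcome per visit.
- **(c)** Protocol 12.1.1 uses the same before/after wording as SAP 11.15, so part of this inconsistency lies within the protocol.

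**Conclusion.** The definition is wrong as written and should be fixed. By the SAP's own labels, category 7 belongs neither in suicidal behavior nor in the combined outcome. The error can only raise those two counts and lower the count of subjects with neither; the ideation line is unaffected.

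The size depends on at least one subject answering yes to category 7 and no to 6, 8, 9 and 10. No test, power figure or sample size changes. The contradiction itself rests on the text of SAP 11.16 alone; only the per-arm percentages for the 52 subjects rest on an assumed split. Points (a) to (c) are minor alignments.

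**What to change.** In SAP 11.16:

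- Define suicidal behavior as a yes to any of the four categories 6, 8, 9 and 10.
- Define the combined outcome as a yes to any of categories 1-6 or 8-10.
- Report category 7 on its own line, outside both. Removing it from the composites cures the contradiction; the separate line keeps the information visible.

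In the same revision:

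- **(a)** In SAP 12.10.5, change the set from ITT to Safety.
- **(b)** State there that results are given for the post-Baseline period overall and per visit (C-SSRS is scheduled at Weeks 4 and 8), or record the departure in SAP 13.
- **(c)** In SAP 11.15, count as AEs the events that start or worsen with the first VR session or later, in line with Protocol 15.4.3.

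The cost is SAP wording and flag programming. Category 7 is already a separate item, so data collection and study conduct do not change. Change (a) alters no denominator at the cutoff, and the Safety population definition stays as it is.

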11.17 Endpoints

11.17.1 CEQ Scores

The CEQ asks about the improvements that subjects believe will be achieved as a result of treatment, and how believable, convincing, and logical the treatment seems. It contains 6 items (each item is rated on a 1-9 scale). Total CEQ score is calculated for each subject at each visit by taking the sum of score of all 6 items of the scale ranging from 6 to 54. Higher score corresponds to better credibility and expectancy.

CEQ scores will be assessed at Baseline, Week 6 and Week 8. Based on the 6 items, two factors will be derived: the credibility factor and the expectancy factor.

Credibility Score

Credibility score is calculated for each subject at each visit by taking the sum of score of the first 3 items of the scale.

The items which are considered for calculating credibility score are:

- At this point, how logical does the treatment offered to you seem?
- At this point, how useful do you think the treatment will be in reducing your symptoms of social anxiety?
- How confident would you be in recommending this treatment to a friend who experiences similar problems?
- Expectancy Score

Expectancy score is calculated for each subject at each visit by taking the sum of score of the last 3 items of the scale.

The items which are considered for calculating expectancy score are:

- By the end of the therapy period, how much improvement in your symptoms of social anxiety do you think will occur?
- At this point, how much do you really feel that therapy will help you to reduce your symptoms of social anxiety?
- By the end of the therapy period, how much improvement in your symptoms of social anxiety do you really feel will occur?

11.17.2 Subject Retention Rate

Subject retention rate will be derived at Week 6 and Week 8/EOS for each of treatment groups.

Subject Retention Rate at Week 6 or Week 8/EOS =

$$\frac{\text{Number of subjects on the study at Week 6 or Week 8/EOS}}{\text{Total number of subjects in that treatment group}} * 100$$

Note: Subject who do not perform Week 6 but perform Week 8 will still be counted as subjects remaining on the study at Week 6.

11.17.3 Session-wise Time-on-Task

Task time is defined as the required video task time for BES-100 and required elements task time for BVR-100. Time-on-task calculation in each session for BVR-100 and BES-100 is given below:

Week	Session	BVR-100	BES-100
Week 1	Session 1	Required Journey Map Tutorial/SC Practice/Mindfulness Tutorial Task Time	Required Video Task Time + Required Campfire Task Time
	Session 2	Required Intro Cog Reframing Task Time + Required Cog Reframing Tutorial Task Time	Required Video Task Time
	Session 3	Required SC Practice Task Time	The same as Session 2
Week 2 - 8	Session 4 - 24	The same as Session 3	The same as Session 2

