### 6.2. Secondary Endpoint(s)

Secondary endpoints for this study include:

- Subject retention in each group will be assessed by percentage of subjects who remain on the study at Week 6, and Week 8/EOS. Reasons for dropout will be documented.
- Time-on-task, averaged over all VR sessions, will be assessed at Week 6 and Week 8/EOS. Time on task will be automatically recorded by the VR system after each session.

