### Intervention Period

#### Baseline

The Baseline visit will be split into two separate parts. During the first part of the Baseline visit, a telehealth call will be performed with the investigator site staff who will administer Baseline visit (Day 1) assessments including clinician-administered outcome measures (C-SSRS, LSAS, CGI-S), collect any adverse events (AEs), concomitant medication changes, and facilitate the delivery of Patient Reported Outcomes (PROs; PHQ-9). During the second part, after the call with the investigator site staff is completed, subjects will receive access to a video-guided VR onboarding session providing information to set-up the VR headset, guidance for the initial sign-up, and information about the intervention the subject has been allocated to. This session will be completed by the subject without any involvement of the investigator site staff. However, subjects will be able to reach out to an unblinded site support team for any assistance/guidance during the video-guided onboarding session or at any time thereafter. The unblinded site support team will ensure that both the video-onboarding and the first VR session are completed. After completing the video-guided onboarding and the first VR session, subjects will be asked to complete the CEQ.

#### Week 1- Week 8

During Weeks 1 through 8, subjects will be asked to complete at home self-guided VR sessions. Subjects in both groups will be asked to engage in a minimum of three required VR sessions per week, for a period of 8 weeks. The Baseline visit is the first day of Week 1, and after baseline during the rest of the week, a minimum of two additional VR sessions must be completed by the subject. In addition to the required practices, subjects will be encouraged to also engage with optional content and to review content completed in previous sessions. Engagement with both

study interventions will be monitored on a regular basis and notifications will be sent regularly to remind subjects to engage with the interventions. Unscheduled telehealth to complete/perform additional safety assessments be conducted as deemed necessary by the investigator site staff/subject.

During Weeks 1 (aside from the Baseline visit), 3, 5, and 7, there will be no study assessments, or scheduled telehealth calls with investigator site staff completed.

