## 9. STUDY MATERIALS AND MANAGEMENT

### 9.1. Description of Investigational Intervention

BVR-100 is a non-invasive, self-guided, at-home, VR intervention co-developed by BehaVR Inc. and Sunovion Pharmaceuticals, Inc. that is being developed for the treatment of SAD. BVR-100 offers educational modules and immersive environments created using both computer-generated and 360° videos. BVR-100 is delivered via consumer-grade 6 degrees-of-freedom (DoF) VR Head Mounted Device (HMD). The intervention includes immersive and automated VR experiences that guide the user through educational and experiential learning modules.

It is intended as an 8-week program with a recommended minimum frequency of 3 weekly sessions. Each session will be approximately 5-20 minutes long (depending on type and amount of content experienced).

Like BVR-100, BES-100 is a non-invasive, self-guided, multisession, at-home, VR intervention designed to be used as a sham control condition for the evaluation of BVR-100 in the treatment of SAD. BVR-100 and BES-100 are comparable in all technological, design, and programmatic characteristics, except for the mechanisms of action.

The computer-generated environment will be interactive to increase engagement and provide subjects with a similar interactive experience as BVR-100.

Like BVR-100, BES-100 is intended as an 8-week program with a recommended minimum frequency of 3 weekly sessions. In addition to the 3 weekly sessions, users can review any already experienced modules or engage with the distraction module at any point during the program. Each session will be approximately 5-20 minutes long.

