4.5 Treatment Allocation

Subjects will be assigned via an IWRS in a 1:1 ratio to either BVR-100 or to BES-100. A VR headset pre-loaded with either BVR-100 or BES-100 will be shipped to the subject's address.

BVR-100 is a non-invasive, self-guided, at-home, VR intervention which offers educational modules and immersive environments created using both computer-generated and 360° videos. The intervention includes immersive and automated VR experiences that guide the user through educational and experiential learning modules.

BES-100 is a non-invasive, self-guided, multisession, at-home, VR intervention designed to be used as a sham control condition for the evaluation of BVR-100 in the treatment of SAD. BVR-100 and BES-100 are comparable in all technological, design, and programmatic characteristics, except for the mechanisms of action. The computer-generated environment will be interactive to increase engagement and provide subjects with a similar interactive experience as BVR-100.

Both are intended as an 8-week program with a recommended minimum frequency of 3 weekly sessions. Each session will be approximately 5-20 minutes long (depending on type and amount of content experienced).

5 Assessment Schedule

Study Period	Screening	Randomization	Investigational Intervention Use Period				
			Baseline ^a	V4	V5	V6	V7
Study Visit	V1	V2	V3	V4	V5	V6	V7
Study Week	NA	NA	W1	W2	W4	W6	W8 (EOS/ET) ^b
Study Visit Days	Up to 14 days	Up to 7 days	1-7	8-14	22-28	36-42	50-56
Procedure							
Obtain Informed Consent	X						
Review Inclusion/Exclusion Criteria	X	X					
Record Demographics and Baseline Characteristics	X						
Record Medical/ Psychiatric History	X						
Administer MINI	X						
Randomization ^c		X					
Dispense Investigational Intervention via IWRS ^c		X					
Subject Self-guided Weekly VR Sessions ^d			X	X	X	X	X
Clinician Administers the LSAS	X		X	X	X	X	X
Clinician Administers the C-SRSS	X		X		X		X
Subject Completes the PHQ-9 ^e	X		X	X	X	X	X
Subject Completes the CEQ			X			X	X
Clinician Administers the CGI-I				X	X	X	X
Clinician Administers the CGI-S			X	X	X	X	X
Subject Completes the PGI-I				X	X	X	X
Conduct Qualitative Interview ^f							X
Prior/Concomitant Medications	X	X	X	X	X	X	X
Pretreatment Event and Adverse Event Monitoring	X	X	X	X	X	X	X
Subject Returns Investigational Intervention ^f							X
Telephone Contact ^g	X	X	X	X	X	X	X

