7.2 Secondary Endpoints

Secondary endpoints for this study include:

- Subject retention in each group will be assessed by percentage of subjects who remain on the study at Week 6, and Week 8/EOS.
- Time-on-Task, averaged over all VR sessions, will be assessed at Week 6 and Week 8/EOS. Time-on-Task will be automatically recorded by the VR system after each session.

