11.17.4 Average Time-on-Task

Average time on task at Week 6 and Week 8/EOS (and at other weeks as applicable) is calculated as the sum of the task time (calculated as mentioned in section 11.17.3) from each required session completed, divided by the number of required completed sessions at Week 6 and Week 8/EOS.

$$\text{Average Time - on - Task (minutes)} = \frac{\text{Sum of the task time from each required VR session completed at Week } X}{\text{Total number of completed required VR sessions}}$$

X is 1, 2, ..., 8.

Overall average Time-on-Task per session across the entire study will be calculated as

$$\text{Overall Average Time - on - Task (minutes)} = \frac{\text{Sum of the task time from each required VR session completed}}{\text{Total number of completed required VR sessions}}$$

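### Time-on-task is defined over all VR sessions but computed only from completed required sessions, and the SAP does not declare the narrowing

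*SAP*

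**What the plan says.** **Definition.** Protocol 6.2 states: "Time-on-task, averaged over all VR sessions, will be assessed at Week 6 and Week 8/EOS". SAP 7.2 repeats this. Both add that the VR system records the time automatically after each session.

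**Derivation.** SAP 11.17.3 states: "Task time is defined as the required video task time for BES-100 and required elements task time for BVR-100". Its table counts required video time for BES-100, with campfire time added in Session 1 only. For BVR-100 it counts named tutorials and practice elements. SAP 11.17.4 sums this time "from each required session completed, divided by the number of required completed sessions at Week 6 and Week 8/EOS". The weekly formula printed beneath limits its numerator to Week X but puts no week on its denominator.

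**Optional use.** Protocol 7.1 (Intervention Period) says of both arms that "subjects will be encouraged to also engage with optional content and to review content completed in previous sessions". Protocol 9.1 adds for BES-100 that "users can review any already experienced modules or engage with the distraction module at any point during the program".

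**Other usage summaries.** SAP 12.8.2.2 reports active days, total sessions, the overall average and the weekly averages by arm. Required sessions completed (12.9.1), retention (12.8.2.1) and treatment duration (12.7) are also reported by arm.

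**Change control.** SAP section 2 lets the SAP prevail over the protocol's statistical section. It also says that major changes to an endpoint definition or its analysis will appear in a protocol amendment. SAP section 13 lists seven changes, and this is not among them.

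**The concern.** The derivation does not compute the endpoint that both documents state. The precedence rule in SAP section 2 cannot settle the matter, because the SAP disagrees with itself: section 7.2 says one thing and section 11.17.4 another.

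The measure matters because Protocol 4.2 and SAP 2.2 link the sham's face validity to time-on-task, and Protocol 4.3 says the sample size is meant to support its reliable evaluation. Protocol 4.3 also says BES-100 is built with a similar amount and variety of prescribed content, so that expected time-on-task is similar. An average restricted to finished prescribed content looks where the design already aims at similarity. It leaves out the sessions in which a subject gave up partway. If one arm abandons more sessions, the time-on-task row need not show it, and the planned larger trial could take over a sham whose comparability in minutes was judged only on completed sessions.

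**Working it through.** **1. The plan's own figure.** Three sessions a week for 8 weeks gives 3 × 8 = 24. This matches the 24 active days in SAP 11.17.5 and Sessions 1 to 24 in SAP 11.17.3.

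**2. Inputs.** Session length m is 5 to 20 minutes (SAP 4.5), with midpoint 12.5. The usage patterns are assumed, because the documents give no abandonment rate:
- Subject A completes 24 of 24 required sessions.
- Subject B completes 6, abandons 6 at a fraction f of their length, and never starts 12.

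**3. Formulas.**
- SAP 11.17.4: minutes in completed required sessions ÷ number of completed required sessions. A = 24m ÷ 24 = m. B = 6m ÷ 6 = m.
- All started sessions: A = m. B = (6m + 6fm) ÷ 12.

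**4. Results (minutes per session).**

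| m | SAP: A | SAP: B | All started: A | All started: B, f = 0.5 | All started: B, f = 0.25 to 0.75 |
|---|---|---|---|---|---|
| 5 | 5 | 5 | 5 | 3.75 | 3.125 to 4.375 |
| 12.5 | 12.5 | 12.5 | 12.5 | 9.38 | 7.81 to 10.94 |
| 20 | 20 | 20 | 20 | 15 | 12.5 to 17.5 |

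At m = 12.5 and f = 0.5, B = (75 + 37.5) ÷ 12 = 9.38. Total minutes are 24 × 12.5 = 300 for A and 112.5 for B.

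**5. Optional sessions.** Suppose a subject completes 24 required sessions and 12 optional ones, all of 12.5 minutes. The SAP counts 300 of 36 × 12.5 = 450 minutes. With equal lengths the per-session average stays at 12.5 either way, so what is lost here is minutes, not a shift in the average.

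**6. Weekly formula.** Three completed Week 6 sessions of 12.5 minutes total 37.5 minutes. Divided by the 3 sessions of that week, the average is 12.5. Read literally, the printed denominator could be the 18 sessions completed by Week 6 (37.5 ÷ 18 = 2.08) or all 24 (37.5 ÷ 24 = 1.56). The sentence above the formula points to the week's own sessions, so this is a drafting gap, but a programmer could follow either.

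**7. Weeks without use.** A subject with no completed required session in a week has 0 ÷ 0. SAP 9.1.1 allows no imputation, so that subject leaves the week's summary. The weekly mean then describes only those still completing sessions.

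**The case against.** A reader might infer that disengagement cannot show anywhere in this analysis. The documents do not support that. SAP 12.8.2.2 puts active days and total sessions beside the average, and SAP 12.9.1 reports required sessions completed, on which subjects A and B would differ as 24 against 6. Retention and treatment duration are reported too. Optional use does not vanish either: active days count any day with a VR session, and total sessions is not worded as required sessions only. What remains is that none of these carries minutes. Retention also counts a subject who attends calls but has stopped using the headset.

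A reader might also blame the derivation for hiding a difference in session counts. It is not the cause. With 24 against 8 completed sessions of 12 minutes and none abandoned, both arms read 12 minutes under the SAP rule and under the all-sessions wording. Any per-session average ignores the number of sessions. Only totals (288 against 96 minutes) separate them.

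A required-content measure has a rationale in Protocol 4.3, which ties expected time to prescribed content. Both arms count required minutes, and the labels differ because the content differs. Campfire time counting only in BES-100 Session 1 needs an explanation but does not prove bias. Nor can one say that the average merely returns content length, since the documents give no content lengths and do not define completion. These points stand. They limit the concern but do not reconcile SAP 7.2 with 11.17.4.

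Finally, the endpoint is descriptive, secondary and part of a pilot, with no test or margin, so no formal conclusion depends on it.

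**Conclusion.** The concern holds as an undeclared mismatch between the endpoint and its derivation. Minutes outside completed required sessions are dropped, so the average can look equal when one arm abandons more sessions. In the illustration, the SAP rule hides a shortfall of 12.5 − 9.38 = 3.12 minutes per started session, which is 25%; over f = 0.75 to 0.25 it runs from 12.5% to 37.5%. These sizes rest on assumed usage and on equal session lengths. The true frequency of abandoned sessions is unknown, and the documents do not say whether minutes in such sessions are logged.

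The weekly denominator and the undefined weeks are smaller defects in the same section. The change should be made because time-on-task helps to judge the sham, but the remaining usage summaries mean that disengagement as such is not invisible.

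**What to change.** In SAP 11.17.3, 11.17.4 and 12.8.2.2:

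1. Compute the endpoint as worded: logged minutes over all started VR sessions (required, optional, repeated and part-completed), with the same counting rule in both arms.
2. Keep the average over completed required sessions as a named supportive row, with the weekly denominator limited to sessions in Week X.
3. Add a descriptive row of total minutes per ITT subject through Week 6 and through Week 8, with zero for weeks without use. This goes beyond the stated endpoint and should be labelled as an addition.
4. Define a completed session, and list any retained narrowing in SAP section 13.

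The cost is some extra programming on usage that Protocol 6.2 and 10.2 say is recorded electronically. Totals may include idle headset time. Before finalising, confirm that the logs hold minutes for part-completed sessions; if they do not, say so and report the number of such sessions if the system records it.
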